Figure 1. TRICC trial data. Relationship between time to extubation and age in months (top panel). Smoothed regression lines for Placebo and Triostat groups converge just above 5 months of age. Median TTE with confidence intervals is shown by age groups (lower panel).

[figure not shown]
[figure not shown]

Figure 2. TRICC trial data. Kaplan-Meier curves for subjects < 5 months age and subjects age > 5 months. (Statistics by Cox Proportional Hazards): Hazard Ratio for the Triostat group among patients < 5 months was 1.72 (p=0.0216), and for > 5 months 0.60 (p = 0.0220). Below the graph are N at risk, number of extubations, (% intubated).

substantially benefited patients less than 5 months of age by reducing the median time to extubation by 43 hours when compared to placebo (T3-treated median-55 hours; 95% CI, 44–92; Placebo 98 hours; 95% CI, 71–142). The study linked the positive clinical outcome to two potential mechanisms. First, T3 treatment improved cardiac function as assessed by echocardiographic parameters. Second, T3 supplementation promoted a decrease in inotropic agent use even though cardiac function improved (Figure 3). In addition to these results, the trial demonstrated the overall safety of T3 supplementation. TRICC provided data which can and likely has impacted care in these very young patients undergoing surgery for congenital heart diseases. However, the FDA denied application for a labeling change to include this indication as we did not demonstrate efficacy in the entire trial cohort, and the analysis by age was not a pre-specified primary endpoint (0 – 2 years of age was the prespecified primary endpoint). The FDA would not consider a Triostat label change for cardiac surgery based on post-hoc analyses of a specific subgroup. Nor would they consider change in labeling regarding safety without demonstrating efficacy in the entire cohort. Accordingly, the FDA suggested that another prospective trial in the specific age group with potential to benefit from treatment was necessary to apply for a labeling change. Thus, we propose performing a second trial in infants less than 5 months of age. The primary efficacy endpoint will be the affect of T3 supplementation on all patients less than 5 months of age. Randomization will be stratified based on age (< or ≥ 4 weeks). The age strata will be considered separately as secondary analyses.

Study Design and Innovation

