hours from termination of cardiopulmonary bypass to readiness for ICU discharge. The intensivists and investigators agreed to record this endpoint (R-ICU) when both of the following parameters are reached: 1) all inotropic drugs terminated; 2) patient extubated and in no respiratory distress, only oxygen supplied by nasal cannula or mask; 3) If on high flow nasal cannula Max O₂ 4L (0-90d old) or 6L (91d-2y), FiO₂ ≤ 50%:

As noted previously, delayed TTE is a direct predictor of “oral feeding difficulty” resulting in hospital discharge on alternate feeding modes such as nasogastric tube^{23, 24}. Discharge with nasogastric tube reduces quality of life for infants and families. Therefore we will use **discharge on full oral feeds as a secondary quality of life end point**.

In order to assess cardiac endpoint parameters we will use **Low Cardiac Output Syndrome (LCOS) as another secondary endpoint**. This assessment will be completed on a separate CRF for LCOS for the first 36 hours after ICU admission and will include 1) identifying clinical signs/symptoms present in LCOS; 2) identifying all interventions involved in the treatment of LCOS; 3) Pharmacologic Assessment of inotropes/vasopressures

Summary of secondary endpoints

- 1) ICU-LOS
- 2) R-ICU
- 3) Discharge on Oral feeds
- 4) LCOS
- 5) Mortality*
- 6) Mortality and/or mechanical circulation (ECMO)*
 - *The PI anticipates that the study is inadequately powered to detect differences in these endpoints between treatment groups, but they were suggested by the FDA regulators.
- 7) Time to sternal closure for patients with delayed surgical closure

[figure not shown]

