Thus, patients randomized but not receiving study medication will not be included in the analysis. Counting patients who receive at least 1 dose of study drug will improve the scientific validity of the study, and reduce the overall cost and duration of this trial. Patients who receive at least 1 dose will be analyzed according to randomization assignment regardless of the treatment actually received. The TTE distributions will be compared across treatment groups using the Log-Rank test. Time zero will be defined as the time of cross-clamp removal, and span until to the first of death, extubation or 21 days. Patients who die will be censored at the earliest of 21 days or death, and patients who are still intubated at 21 days post-cross clamp removal will be censored at 21 days. Medians and 95% confidence intervals for TTE will be based on the Kaplan-Meier estimate to account for censoring. A sensitivity analysis adjusting for non-patient-related delays will also be performed to determine the impact of these delays, which we expect to be few, on the primary efficacy analysis. Differences in death will be compared using Fisher's Exact Test.

Secondary endpoints as previously described will be analyzed using similar methodology. Endpoints with censored observations will be addressed using survival analysis techniques to account for censoring.

This study is powered to detect a hazard ratio of 1.8 with respect to TTE in patients less than 4 weeks of age (assuming half of the total sample is in this age range). The effect in patients < 4 weeks of age is an important clinical outcome as these are the sickest patients in the population, and reduction in their relatively long intubation times provides more opportunity for benefit. There will be no Type I error adjustment for this subgroup analysis in order to maximize power for the primary outcome, but the sample size was determined considering the need to report the effect in the youngest patients. Thus, this analysis will be considered supportive and will be described as such in subsequent publications.

Patient characteristics and adverse events will be compared using the chi-square test or Fisher's Exact test as appropriate. Continuous characteristics and outcomes will be compared using the T-test or ANOVA for repeated measures. Point estimates for hazard ratios and 95% (2-sided) confidence intervals will be reported.

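### Time to extubation is summarised by Kaplan-Meier alone with deaths censored; the cumulative incidence of extubation, with death as a competing event, should be reported beside it (minor)

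*Combined protocol and SAP*

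**What the plan says.** All of the relevant rules are in the Statistical Analysis section of the combined protocol and SAP.

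- TTE runs from cross-clamp removal to extubation, death or day 21, whichever is first. On deaths: "Patients who die will be censored at the earliest of 21 days or death".
- The summary of the distribution: "Medians and 95% confidence intervals for TTE will be based on the Kaplan-Meier estimate to account for censoring".
- Treatment groups are compared by a Cox model with terms for the stratification factors and delayed sternal closure, and by the log-rank test.
- One sensitivity analysis for TTE is planned, on another subject: "A sensitivity analysis adjusting for non-patient-related delays will also be performed".
- Death has its own comparison: "Differences in death will be compared using Fisher's Exact Test". The Summary of secondary endpoints also lists mortality, and mortality and/or ECMO.

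Nowhere do the documents plan a competing-risk summary of TTE, a cumulative incidence, or an alternative handling of death. They do not describe the Cox result as cause-specific.

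**The concern.** Kaplan-Meier treats a censored infant as one who could still be extubated later, at the same rate as those still intubated. That is reasonable for an infant whose follow-up simply ends. It is not possible for one who has died. With deaths censored, one minus Kaplan-Meier therefore lies above the proportion actually extubated as soon as any infant dies intubated. This follows from the definition and does not require deaths to be related to readiness for extubation.

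What is at stake is the meaning of a reported number. TTE is the endpoint meant to support a labelling change, and the background section presents the TRICC benefit as a difference in medians: "by reducing the median time to extubation by 43 hours when compared to placebo". Readers will take the TRICC-2 median as the time by which half of the infants were off the ventilator, and strictly it is not.

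The Secondary Endpoints section describes mortality as very low, citing 5.3% and 3% for the whole TRICC cohort aged 0 to 2 years. Among infants under 5 months, the population of this trial, Table 3 gives 4 of 50 (8.0%) on placebo and 3 of 48 (6.3%) on Triostat.

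**Working it through.** **The plan's own figure first.** The plan gives power above 80% for 220 infants at a hazard ratio of 1.55, two-sided 5%, 1:1 allocation.

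- Events needed (Schoenfeld): 4 × (1.960 + 0.842)² / (ln 1.55)² = 4 × 7.849 / 0.1921 = 163.5, so 164.
- With 220 extubations, power is 90.2%.
- The pooled TRICC death rate under 5 months is 7/98, so 220 × 7/98 ≈ 16 deaths. If all of them came before extubation, 204 extubations would remain and power would be 87.9%.

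The stated power is met, and censoring deaths does not threaten it.

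**Inputs for the TTE summary.**

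- Medians of 98 h (placebo) and 55 h (T3), from the Significance section. I take these to be Kaplan-Meier medians, because the accompanying Figure 2 shows "Kaplan-Meier curves for subjects < 5 months age and subjects age > 5 months".
- Horizon of 21 days = 504 h.
- Share p dying before extubation. Table 3 counts deaths at any time on study and does not split them by extubation status. The full rates (8% placebo; 3/48 = 6.25% T3) are therefore upper assumptions, and 2% is an assumed lower value.

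**Formulas, constant hazards.** Extubation hazard he = ln 2 / median. Death hazard hd = he × p/(1 − p), so that a share p dies before extubation, and he/(he + hd) = 1 − p.

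- Kaplan-Meier level at day 21: 1 − exp(−504 he).
- Cumulative incidence at t: (1 − p) × [1 − exp(−(he + hd) t)].
- Time to 50% extubated: t = −ln[1 − 0.5/(1 − p)] / (he + hd).

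**Worked case, placebo, p = 8%.** he = 0.6931/98 = 0.007073 per hour; he + hd = 0.007073/0.92 = 0.007688. Then t = −ln(1 − 0.5/0.92)/0.007688 = 0.7841/0.007688 = 102.0 h.

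| Arm | Deaths before extubation (assumed) | Kaplan-Meier median | Time to 50% extubated | Day 21, one minus Kaplan-Meier | Day 21, cumulative incidence |
|---|---|---|---|---|---|
| Placebo | 2% | 98 h | 98.9 h | 97.2% | 95.4% |
| Placebo | 8% | 98 h | 102.0 h | 97.2% | 90.1% |
| T3 | 2% | 55 h | 55.5 h | 99.8% | 97.9% |
| T3 | 6.25% | 55 h | 56.7 h | 99.8% | 93.6% |

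The gap between arms is 98 − 55 = 43 h by Kaplan-Meier. By cumulative incidence it is 98.9 − 55.5 = 43.4 h at the lower rate and 102.0 − 56.7 = 45.3 h at the upper rates.

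**Timing.** Constant hazards spread deaths over follow-up. If instead all the assumed deaths fall at one time:

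- Placebo, 8%: the time to 50% extubated is 108.6 h for deaths at 24 h, 102.5 h for deaths at 72 h, and 98 h for deaths at or after 98 h.
- T3, 6.25%: it is 58.6 h for deaths at 24 h, 56.0 h at 48 h, and 55 h at 72 h or later.

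**The primary test.** In a simulation of 110 infants per arm (6,000 runs), with deaths before extubation at 8.0% and 6.25% and independent of extubation, the log-rank test with deaths censored had 87.4% power at a hazard ratio of 1.55. It rejected in 5.7% of runs at a hazard ratio of 1.0, close to nominal.

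**The case against.** The case for leaving the plan alone is fair in most respects. Death is not ignored: it is compared by arm and appears in two secondary endpoints. The shift in the medians, at most 4.0 h and 1.7 h under constant hazards, is small beside the TRICC confidence intervals of 71-142 h and 44-92 h. The shift is zero if every death while intubated follows the median. All of this stands, and it is why the point is minor. But a separate death table does not correct the TTE summary, and the median keeps a meaning slightly different from the one readers will give it.

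Several stronger readings are tempting, and the documents do not support them:

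- *The primary analysis is biased.* It is not. Cox and log-rank analyses with deaths censored are valid for the cause-specific hazard of extubation.
- *Extubation at day 21 will be overstated by up to 7 points.* This holds only if someone reads that proportion from Kaplan-Meier. The plan promises medians and intervals, not a TRICC-2 curve or a day-21 percentage.
- *A favourable hazard ratio could hide no gain in infants extubated alive.* Cases can be built with 6.25% deaths on placebo and 8% on T3, but they need a T3 death hazard about 1.57 times placebo at a hazard ratio of 1.2, or 2.02 times at 1.55. TRICC deaths ran the other way.
- *The secondary endpoints share the fault.* The plan says only "Endpoints with censored observations will be addressed using survival analysis techniques to account for censoring" and does not state how deaths are treated there.
- *Infants who die should be held as not extubated to day 21 in a further analysis.* That is a debatable choice of estimand with low power (about 44-71% in simulation at the design effect), not something the plan lacks by error.

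**Conclusion.** The point holds as a minor one. As written, the rule gives a median that is too short whenever an infant dies intubated before it. Under constant hazards, and with 2% up to the full Table 3 rates assumed to die before extubation, the understatement is 0.9-4.0 h on placebo and 0.5-1.7 h on T3. Any day-21 proportion taken from Kaplan-Meier would be about 2-7 points too high.

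These sizes rest on the assumed shares, because the documents give neither the number nor the timing of TRICC deaths before extubation. Defining the 8% as deaths by day 21, rather than as deaths at any time before extubation, changes the placebo upper case only to 89.9% and 102.1 h.

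A reader might infer that Kaplan-Meier flatters T3. Under constant hazards it does not: 43 h against 45.3 h at the upper rates. The direction does depend on timing. If the T3 deaths all fell at 24 h and the placebo deaths all after 98 h, the gap would be 98 − 58.6 = 39.4 h. Nothing in the documents points to such a pattern. The primary test, its power and the sample size are unaffected.

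**What to change.** Keep the Cox and log-rank analyses with deaths censored as primary, and label the Cox result a cause-specific hazard ratio. Keep the Kaplan-Meier medians so that results can be set beside TRICC. In Statistical Analysis, directly after the Kaplan-Meier sentence, add:

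> Cumulative incidence of extubation to day 21, with death before extubation as a competing event, will also be estimated by arm (Aalen-Johansen), with the time it reaches 50% and its 95% CI, and the number of deaths before extubation per arm.

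The cost is a sentence and a label in the plan and a little more analysis. No new data are needed, since the Schedule of Events already has the dates and times of extubation and death recorded. The downsides are two sets of medians to explain and slightly less favourable summary figures. The wording should be settled before unblinding, so that the added summary is not a post-hoc choice.

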Appendix 1: Listing of Expected AE's

1. Cardiac General
 - 1.1 Arrhythmia (recorded if requires medication or treatment)
 - 1.1.1 Atrial fibrillation
 - 1.1.2 Atrial flutter
 - 1.1.3 Supraventricular tachycardia
 - 1.1.4 Junctional ectopic tachycardia
 - 1.1.5 Sinus node dysfunction (requiring pacing)
 - 1.1.6 Atrioventricular block(second or third degree)
 - 1.1.7 Ventricular tachycardia
 - 1.1.8 Ventricular fibrillation
 - 1.2 Mediastinum
 - 1.2.1 Hemopericardium (requiring intervention, includes postoperative mediastinal hemorrhage)
 - 1.2.2 Pericardial effusion (requiring drainage)
 - 1.2.3 Postpericardiotomy syndrome (requiring treatment)
 - 1.3 Cardiac performance
 - 1.3.1 Hypotension (<40 mm Hg for neonates; <50mm Hg after stage II surgery)
 - 1.3.2 Hypertension (requiring long-term therapy, ie, >30 days after discharge, therapy should be at the therapeutic doses and specifically prescribed for the treatment of hypertension)
 - 1.3.3 RV dysfunction(requiring escalation or initiation of therapy, not to include immediate postoperative dysfunction routinely associated with cardiopulmonary bypass)
 - 1.3.4 Semilunar valve insufficiency or stenosis (requiring treatment initiation or escalation)
 - 1.3.5 Atrioventricular valve insufficiency or stenosis (requiring treatment initiation or escalation)
 - 1.3.6 Prosthetic valve dysfunction
 - 1.4 Great vessels
 - 1.4.1 Superior vena cava stenosis (anatomic, symptomatic, "superior vena cava syndrome")
 - 1.4.2 Superior vena cava occlusion
 - 1.4.3 Inferior vena cava occlusion
 - 1.4.4 Other cardiovascular
2. Respiratory
 - 2.1 Chronic respiratory failure (intubated for >2 weeks after surgery)
 - 2.2 Chylothorax (postoperative accumulation of chylous fluid in the pleural space requiring intervention whether by evacuation, dietary change, and /or medical treatment)
 - 2.3 Hemothorax (requiring drainage)
 - 2.4 Phrenic nerve injury/diaphragmatic paralysis (newly elevated diaphragm on chest x-ray film)
 - 2.5 Pleural effusion (requiring drainage >7 days after surgery, other)
 - 2.6 Pneumothorax (requiring tube insertion)
 - 2.7 Tracheal injury
 - 2.8 Vocal cord injury (direct visualization)
 - 2.9 Airway obstruction (requiring a significant intervention)
 - 2.10 Hypoxia (requiring readmission or escalation of care)
 - 2.11 Other respiratory
3. Neurologic
 - 3.1 Choreoathetosis/posturing (moderate involuntary movements interfering with function)
 - 3.2 Coma

- 3.3 Intracranial bleeding (confirmed by imaging)
 - 3.4 Seizure(s) (confirmed by electroencephalogram or obvious motor signs)
 - 3.5 Stroke (confirmed by imaging study)
 - 3.6 Hydrocephalus (report if CTCAE grade >2)
 - 3.7 Neurologic deficit persisting at discharge not attributed to any of the above diagnoses
 - 3.8 Other neurologic
 - 4. Gastrointestinal
 - 4.1 Direct bilirubin >4 umol/L
 - 4.2 Liver failure (AST, ALT, or GGT > 500 U/L)
 - 4.3 Necrotizing enterocolitis, confirmed (pneumatosis or free air)
 - 4.4 Necrotizing enterocolitis, suspected (NPO, antibiotics started)
 - 4.5 Other esophageal or bowel perforations not associated with necrotizing enterocolitis
 - 4.6 Upper gastrointestinal bleed, requiring treatment
 - 4.7 Stricture/stenosis (CTCAE > grade 2)
 - 4.8 Other gastrointestinal
 - 5. Infectious
 - 5.1 Empyema
 - 5.2 Endocarditis
 - 5.3 Gastroenteritis or enteritis
 - 5.4 Line infection, bacterial (positive blood cultures)
 - 5.5 Line infection, fungal (positive blood cultures with initiation of therapy)
 - 5.6 Pneumonia, respiratory infection, viral (requiring the initiation of therapy)
 - 5.7 Mediastinitis/wound infection, deep (requiring incision and drainage; sternal instability)
 - 5.8 Wound infection, superficial (erythema, possible tissue separation and drainage)
 - 5.9 Sepsis, confirmed (positive blood cultures, not line infection)
 - 5.10 Sepsis, clinical with negative cultures
 - 5.11 Urinary tract infection
 - 5.12 Other infection
 - 6. Renal
 - 6.1 Acute renal failure (creatinine> 1.5mg/dL (133umol/L) or tripling of baseline value for <7 days; temporary dialysis)
 - 6.2 Chronic renal failure (creatinine >1.5mg/dL (133 umol/L) or tripling of baseline value for >7 days; long-term dialysis)
 - 6.3 Other renal
 - 6.4 Hematologic Anemia (hemoglobin <10 gm/L)
 - 6.5 Thrombocytopenia (platelets < 50 x 10⁹/L)
 - 6.6 Hematoma (CTCAE grade > 2)
 - 6.7 Hemorrhage, gastrointestinal (CTACE grade >2; hemepositive stools)
 - 6.8 Hemorrhage, genitourinary (CTCAE grade > 2)
 - 6.9 Hemorrhage, pulmonary/upper respiratory (CTCAE grade > 2)
 - 6.10 Other hematologic
 - 7. Vascular
 - 7.1 Thrombus/thromboembolism
 - 7.2 Vascular, other
 - 8. Other complication
 - 9.1 Other
-

RV, Right Ventricular; CTCAE, Common Terminology Criteria for Adverse Events; AST, aspartate aminotransferase; ALT, alanine aminotransferase; GGT, gamma-glutamyl transferase; NPO, nothing by mouth.

Citations

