Safety endpoints include arrhythmias, infection rate, serious, and non-serious adverse events. Only treatment-emergent events with signs or symptoms that begin or worsen after the first dose of study drug will be reported.

Total T3 levels will be analyzed to determine half-time using a single compartmental pharmacokinetic model similar to previously published methodology by the PI ²⁹.

Safety

Adverse Event (AE) Reporting

Reporting of adverse events in cardiac surgical trials in infants is complicated as there is no regulatory guidance specific to conducting clinical research in critically ill children. The Pediatric Heart Network reported a new method of reporting using predefined "sentinel events" in place of serious adverse events (SAEs). All other adverse events were reported as "complications". The standard definitions using "Common Terminology Criteria for Adverse Events" (CTCAE), developed by the National Cancer Institute does not carry enough appropriate pediatric codes to cover the complexity of the postsurgical population. The Pediatric Heart Network (PHN) launched the Single Ventricle Reconstruction Trial and midway switched from standard reporting to their new system identifying "sentinel events"^{30, 31}. This system reduced administrative burden and improved quality of safety reporting. However, their study which evaluated surgical techniques against one another was not performed under IND and according to PHN investigators their system has not been reviewed by the FDA. On query regarding the appropriateness for using the PHN published method for reporting adverse events in a drug trial the FDA responded: *"Our goal is to understand the effect of said study treatment on adverse events, i.e., "adverse reactions" (to study drug), not to catalog all bad things that happen to subjects. In this respect, the process PHN followed may or may not be reasonable. One would need to think through whether the experimental treatment had any likelihood of affecting the common adverse events associated with surgery and whether the investigators were likely to be able to distinguish study treatment-related events from "normal" (clinically expected) ones."*

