As TRICC-2 will be performed with IND requirements, we will need to report adverse events (AEs) using FDA standards revised by the common rule amendments of 21 CFR Parts 312 and 320 (April 2011). The common rule does reduce reporting requirements somewhat as long as expected AEs and SAEs are predefined in the study protocol (see Appendix 1). A summary of adverse events reported for the TRICC trial appears in Table 3. This shows that the majority of patients show AEs, though relatively few have SAEs using standard reporting methodology. Thus, the greatest burden for reporting may not be related to SAEs but to reporting of common procedural complications as AEs regardless of severity. Using literature review and expert consensus, the PHN developed lists defining common and specific AEs which occur in this infant population undergoing cardiac surgery. Protection of Human Subjects (section 6) contains a list adapted from the PHN,

which defines expected surgical complications or AEs. For instance pleural effusion is defined as an adverse event when drainage exceeds 7 days after surgery. This definition will reduce reporting of pleural effusions. In an effort to address the issue raised by the FDA with regard to affect on common adverse events in this population, we have numerically coded the complication table generated by the PHN (section 6).

Summary of Adverse Events from Time of Surgery to the First of Hospital Discharge, 30 Days Post-procedure or Death for entire cohort and < 5 months						
	Placebo Total (N=95)	Triostat Total (N=98)	P	Placebo, < 5 months (N=50)	Triostat, < 5 months (N=48)	P
At Least One AE	82 (86.3%)	80 (81.6%)	0.376	45 (90.0%)	42 (87.5%)	0.695
At Least One Serious AE	12 (12.6%)	14 (14.3%)	0.736	8 (16.0%)	8 (16.7%)	0.929
At Least One Unexpected AE	40 (42.1%)	40 (40.8%)	0.856	25 (50.0%)	22 (45.8%)	0.68
At Least One Possibly Treatment-Related AE	45 (47.4%)	57 (58.2%)	0.151	26 (52.0%)	34 (70.8%)	0.065
Death (any time on study)	5 (5.3%)	3 (3.1%)	0.493	4 (8.0%)	3 (6.3%)	1
Death or Mechanical Life Support	5 (5.3%)	3 (3.1%)	0.493	4 (8.0%)	3 (6.3%)	1
Arrhythmia AE	9 (9.5%)	11 (11.2%)	0.69	7 (14.0%)	7 (14.6%)	0.934
JET	7 (7.4%)	8 (8.2%)	0.837	5 (10.0%)	5 (10.4%)	0.946
SVT	2 (2.1%)	3 (3.1%)	1	2 (4.0%)	2 (4.2%)	1
VT	1 (1.1%)	0 (0.0%)	0.492	1 (2.0%)	0 (0.0%)	1

Table 3. TRICC data. Table shows no significant difference in rates of adverse events between placebo and Triostat groups. Postoperative arrhythmias served as an index safety factor.

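### Appendix 1 item 6.4 sets the anaemia limit at hemoglobin below 10 g/L, which is 1 g/dL, so as written the item captures essentially no anaemia

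*Combined protocol and SAP*

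**What the plan says.** Item 6.4 of Appendix 1 reads "Hematologic Anemia (hemoglobin <10 gm/L". It is the only hemoglobin limit in the protocol and SAP, and no other section restates or corrects it.

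The list has a function in the plan. Under Safety, Adverse Event (AE) Reporting, the protocol says that IND reporting is somewhat reduced "as long as expected AEs and SAEs are predefined in the study protocol (see Appendix 1". The same section describes a list adapted from the Pediatric Heart Network "which defines expected surgical complications or AEs". It gives pleural effusion as an example of how a definition limits what is recorded: "This definition will reduce reporting of pleural effusions". Statistical Analysis then states: "Safety endpoints include arrhythmias, infection rate, serious, and non-serious adverse events", and plans chi-square or Fisher's exact tests on adverse events.

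Three other items in Appendix 1 bear on the point:
- Item 6.1 gives its limit in two unit systems: "Acute renal failure (creatinine> 1.5mg/dL (133umol/L) or tripling of baseline value for <7 days; temporary dialysis".
- The last hematologic entry is open-ended, with no limit: "6.10 Other hematologic".
- Item 4.1 is a laboratory limit in one unit only: "Direct bilirubin >4 umol/L".

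**The concern.** An adverse event definition with a laboratory cut-off works as a recording rule. If the cut-off lies where no patient will be, the item stays empty whatever the true frequency of anaemia.

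Site staff then have three choices. They can follow the text and record nothing under 6.4, use the open item, or assume that another unit was meant. The protocol does not say which, and the trial has three centers.

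Two things are at stake. The first is consistent ascertainment of one non-serious event type. The second is its status under the IND: an anaemia that a site reports but that does not meet the predefined definition is neither clearly expected nor clearly unexpected. The earlier TRICC trial reported that distinction (Table 3 has a row for patients with at least one unexpected event), so it is likely to be used again.

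**Working it through.** **Inputs.** Hemoglobin limit 10 g/L (Appendix 1, item 6.4). Creatinine limit 1.5 mg/dL, also printed as 133 umol/L (items 6.1 and 6.2). The molar mass of creatinine, 113.12 g/mol, is an outside constant and not in the documents.

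**1. Does the list handle units correctly elsewhere?** Creatinine in umol/L = (mg/dL × 10 / molar mass) × 1000.

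1.5 × 10 / 113.12 × 1000 = 132.6 umol/L, which rounds to the printed 133.

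The list's own two-unit figure is reproduced.

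**2. Convert the hemoglobin limit.** 1 L = 10 dL, so g/dL = (g/L) / 10.

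10 g/L / 10 = 1.0 g/dL.

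**3. Size of the slip if g/dL was meant (assumption).** 10 g/dL × 10 = 100 g/L. The ratio to the printed limit is 100 / 10 = 10.

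**4. Does the definition control recording?**
- The pleural effusion example under Adverse Event (AE) Reporting shows a definition being used to reduce what is reported.
- Other Appendix 1 entries work the same way: arrhythmias (1.1) count only if treated, and hydrocephalus (3.6) only above a stated CTCAE grade.
- Item 6.4 has the same form, so its limit is meant to be applied.

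**5. Is there another route for anaemia?** Yes. Item 6.10 has no limit, the list closes with a general category for other complications, and Statistical Analysis does not restrict adverse events to listed items. None of these sets a threshold, so none yields counts that are comparable between sites.

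**The case against.** The strongest reply is that this is an obvious slip which clinical staff will read through, and that anaemia has other places to go. Part of that stands. A reader might infer that anaemia vanishes from the safety data. The documents do not support this, because item 6.10, the closing general category and the unrestricted safety endpoints all leave it reportable. What remains is that these routes have no limit, and that relying on staff to correct the unit themselves is undocumented and may differ by site.

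A reader might also infer a biased comparison between arms. That does not follow either. Under Blinding and Randomization, allocation is blocked to keep the arms equal within each center and treating physicians are blinded. Different readings by site should therefore fall on both arms alike.

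It can further be said that the sentence about a list defining expected complications points to section 6 of Protection of Human Subjects, which is not in the text available, and not to Appendix 1. That is fair. The two lists are probably the same, but this is an inference. The point does not depend on it, because the protocol cites Appendix 1 directly for predefining expected events.

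Finally, it is tempting to call item 4.1 a second unit error. Nothing in the documents contradicts the bilirubin limit, and the source list cannot be seen. A cut-off that is too low there would also act in the other direction, towards more recording. It supports a request to verify and nothing further.

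An extraction fault cannot be fully excluded, but mg/dL came through intact in items 6.1 and 6.2.

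**Conclusion.** The point holds for item 6.4. The printed limit equals 1.0 g/dL and, followed as written, captures essentially no anaemia. It is ten times too low if g/dL was intended.

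The consequence is lost or inconsistent ascertainment of one adverse event across sites, and unclear classification as expected or unexpected. The primary endpoint, power and type I error are untouched, and no bias between arms is expected.

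The conversion is exact. Two assumptions come from outside the documents: that a value below 1 g/dL is not seen in a living infant, and that the cause is a unit slip. The second is made likely, but not proved, by the correct creatinine conversion in the same list. The correction should be made because the list is operative and the change is small.

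**What to change.** Reconcile item 6.4 with the list it was adapted from and correct the unit accordingly. Print the limit in both unit systems, as the creatinine items do, and send sites a notice with the corrected page. In the same pass, verify the unit of item 4.1 against the source and change it only if the source differs. If section 6 of Protection of Human Subjects carries a separate copy of the list, make the two agree.

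The cost is a one-line change to the appendix and a site notice. Looking back through laboratory values for patients already enrolled would be a separate and larger task. The protocol does not name hemoglobin among the data to be captured, although case report forms not included here may collect it, so that step is not part of this recommendation.
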